Patients initially receive 2 cycles of treatment. Based on an individual benefit-risk assessment, 3 additional cycles of Blincyto consolidation treatment may be considered if complete remission has been achieved. A single cycle of treatment is 4 weeks of continuous infusion and each cycle of treatment is separated by a 2 week treatment-free interval.

Blincyto safety profile

During the marketing authorisation application, two important safety risks were identified to require additional risk minimisation measures (aRMMs): neurological events and the potential for medication errors (MEs).

Neurological events such as fits, problems with speech, alterations in consciousness, confusion and disorientation, problems with balance and coordination occur in approximately 50% of patients treated with Blincyto (Topp et al. 2015).

Blincyto is infused continuously using a pump device. Hospitalisation is recommended for initiation at a minimum for the first 9 days of the first cycle and the first 2 days of the second cycle **(and also subsequent cycles)**. Blincyto may be administered at home after discharge with an ambulatory pump. Medication errors can occur at any time during the reconstitution, dilution and administration of Blincyto that may result in patients receiving a dose that is too high or too low. Mistakes in setting up the pump, or problems with the pump can also cause MEs. In the pivotal Phase II trial that led to the approval of Blincyto in the EU, MEs were observed in CCI of subjects. In the pooled safety dataset, which includes CCI patients exposed to Blincyto in C studies of different indications, MEs were reported in CCI of subjects. The following MEs were reported: CCI

Overdoses were primarily due to infusion pump errors and Blincyto preparation errors. Most MEs did not result in an adverse event. Of the ones associated with adverse

events, most events were consistent with the known safety profile, mild in severity, and resolved.

Examples of medication errors related to the wrong usage of Blincyto by patient/caregivers include overdose due to pump setting problems, infusion bag placed on the counter to warm it up and pump turned off when the pump alarms low battery.

Blincyto additional risk minimisation

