Haemato-oncologists/nurses in participating centres will include patients and their associated caregivers who fulfil all the selection criteria listed below in a consecutive manner according to the date of initiation of treatment with Blincyto until reaching the target number of patients/caregivers to be recruited per centre. Caregivers can be a spouse, family member, friend or professional helper who has helped with Blincyto treatment. The consecutive selection of patients and caregivers at each site is designed to minimise selection bias and to allow for the study results to be generalisable to the entire population of Blincyto treated patients. To assess generalizability of the data, sites will be asked to keep a log of anonymized demographic profiles (age and sex) of patients administered Blincyto, and their caregivers.

CCI

[figure not shown]
Figure 1. Illustration of sampling strategy

Patients/caregivers who agree to participate in the study with informed consent will be asked to complete a paper questionnaire after discharge from hospital **preferably** when they return to clinic for a bag change or monitoring (Figure 2). Both the patient and the caregiver will be invited to participate in the survey: **however, one can participate without the participation of the other**. If the patient is not well enough to complete the questionnaire on returning to clinic after hospital discharge on Blincyto, the patient will be asked again at the next visit. If a caregiver is not available at a visit, they will be asked at the next available visit to participate. Only one caregiver per patient will be recruited.

Appropriate measures will be adopted to ensure physicians do not influence patient/caregiver's choices (e.g. patients and caregivers will place their completed questionnaires in a sealed envelope).

Figure 2. Illustration of treatment characteristics and questionnaire administration

Note: Patients/Caregivers will complete the questionnaire based upon their first exposure to Blincyto at home. However, the questionnaire may be administered subsequent to blincyto cycle 1

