9.2.3 Subject Eligibility

9.2.3.1 Inclusion Criteria

- Patient/caregiver **completing questionnaire** is 18 years of age or older.
- Patient and/or caregiver of a patient with Ph- R/R B-precursor ALL who has received Blincyto **as an outpatient**.
- Patient/caregiver **completing questionnaire** can read and understand the native language of the country in which the study is being conducted.

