9.2.3.2 Exclusion Criteria

- Patient and/or caregiver of a patient who has only received Blincyto as an in-patient **only**.
- Patient/caregiver is currently employed by Amgen/delegate.
- **Patient and/or caregiver of a patient who is participating in Blincyto clinical trials or is receiving Blincyto through a compassionate use program**

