9.7.2.3.1 Description of Study Enrollment

The study populations as identified in the recruitment process will be described. Recruitment rates and a description of the number of patients/caregivers in the study and analysis populations will be provided.

Analysis sets: As shown in [Figure 3](#), datasets for analysis will be further described in the SAP and will include:

- Study population: All adult patients with R/R Ph- B-precursor ALL initiating Blincyto (or their caregivers).
- Eligible Set: All patients/caregivers who fulfill the eligibility criteria.
- Enrolled Set: All eligible patients/caregivers who agree to participate in the study.
- Full Analysis Set: All patients/caregivers who complete the questionnaire of their corresponding survey and have valid responses to allow for the assessment of the primary objective.
- Safety Set: This is the same as the Enrolled Set.

Figure 3. Study Population and Datasets flow-chart

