9.9 Limitations of the Research Methods

The number of patients willing/able to participate in the survey may be lower than expected because of the severity of the condition and complications during **treatment with Blincyto**: neutropenic fever, infections, and neurological side effects. Responses by caregivers may be anticipated to be different (better?) than patients, as they are often more attentive of the details of the management of their family member or friend, especially in these patients, many of whom will experience side effects and be quite ill during their therapy with Blincyto. This will be assessed by analyzing patients and caregivers separately.

The questionnaire has been designed to facilitate completion by the patient/caregiver on paper. For this reason, some of the questions that address secondary endpoints refer to 'educational materials' in general (e.g. understanding, usage) and do not allow drawing conclusions for each type of material i.e. card and brochure. However, most of the questions apply only to the brochure and some of the questions apply only to the card.

The survey will exclude patients (caregivers of patients) who have only received Blincyto in hospital. This restriction will result in a more meaningful assessment as only patients/caregivers who have the chance to have used the materials will be included; materials are mainly used in the outpatient setting where MEs are more likely to occur. In

addition, the completion of the survey by the patient/caregiver will be restricted to the period after discharged from hospital and ambulatory treatment at home. This time interval is expected to allow sufficient time for the provision and usage of the materials, and the occurrence of MEs (if any), without hindering recruitment.

The survey may be affected by selection bias within centres and non-participation. Consecutive recruitment based on treatment initiation during the study period will be used to avoid selection bias. A log of patients initiating Blincyto during the study period will be kept to check this recruitment process.

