Appendix F. Educational materials

Bincyto Patient Card

Version 1.0

BLINCYTO® (blinatumomab) Approved: September –2015

Educational Brochure for Patients and Caregivers

Patient Card

Please show this card to all emergency and healthcare providers

Information about BLINCYTO® ▼ (blinatumomab)

My name is _____

I am being treated with BLINCYTO a treatment for relapsed/refractory acute lymphoblastic leukemia, which can lower my immune system.

I started treatment on _____

Before providing any treatment, please call my prescribing physician at the number below. If any medical evaluations are undertaken, please provide copies of all medical records, including any treatments and/or test results, to the doctor(s) named below.

	Name	Hospital	City	Phone Number
Haematologist				
Oncologist				
Haematology Nurse				

▼ This medicine is subject to additional monitoring. This will allow quick identification of new safety information. You can help by reporting any side effects you may get to <##>. By reporting side effects, you can help provide more information on the safety of this medicine.

Bincyto Educational Brochure for Patients and Caregivers

Version 1.0

BLINCYTO[®] ▼ (blinatumomab) Approved: September-2015

Educational Brochure for Patients and Caregivers

BLINCYTO[®] ▼ (blinatumomab)

Important Risk Minimisation Information for Patients and Caregivers

This educational brochure contains important information you should know before receiving BLINCYTO.

This educational material is essential to ensure the safe and effective use of the drug and appropriate management of the important selected risks. Please read it carefully before taking the medicinal product.

If you have any questions about BLINCYTO please speak to your doctors or nurses, or refer to the Patient Leaflet, provided with this brochure.

▼ This medicine is subject to additional monitoring. This will allow quick identification of new safety information. You can help by reporting any side effects you may get to <##>. By reporting a side effect, you can help provide more information on the safety of this medicine.

This information is not intended to take the place of discussions with your doctor or other healthcare professionals who are treating your relapsed/refractory Philadelphia chromosome negative acute lymphoblastic leukemia. Read the BLINCYTO patient leaflet provided to you by the doctors or nurses, as well as this educational brochure.

Version 1.0

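### Section 9.2.2 claims the results generalise to everyone treated with Blincyto, but eligibility is limited to outpatient exposure, so the receipt result covers only people treated at home

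*Protocol*

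**What the plan says.** **The claim.** Under patient/caregiver selection, section 9.2.2 gives consecutive recruitment two purposes: to limit selection bias and "to allow for the study results to be generalisable to the entire population of Blincyto treated patients". The ENCePP checklist (Appendix B, item 2.1.3) points to sections 4 and 9.2 for the population to which results are to be generalised, so this sentence is where a reader is sent.

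**Who can enter.** Section 9.2.3.1 requires outpatient exposure. Section 9.2.3.2 excludes the complement: "Patient and/or caregiver of a patient who has only received Blincyto as an in-patient". The Abstract repeats both criteria.

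**Why the excluded group can exist.** Section 7.1 presents home treatment as optional: "Blincyto may be administered at home after discharge with an ambulatory pump".

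**The disclosure.** Section 9.9 states: "The survey will exclude patients (caregivers of patients) who have only received Blincyto in hospital". Its reasons are that those kept had a chance to use the materials, and that use and medication errors belong mainly to the outpatient setting.

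**The analysis sets.** The list in 9.7.2.3.1 opens with a study population of "All adult patients with R/R Ph- B-precursor ALL initiating Blincyto (or their caregivers"), and then narrows to an Eligible Set.

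**The materials.** Table 1 in section 7.1 gives the target of both brochure and card as leukaemia patients receiving Blincyto and their caregivers, with no limit by setting. The brochure in Appendix F opens: "This educational brochure contains important information you should know before receiving BLINCYTO".

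**The endpoint.** Receipt is a primary endpoint (9.3.2, 9.7.2.4). The first research question in section 8 asks whether the safety information reached its target population.

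**The concern.** The generalisability sentence credits consecutive selection with something it cannot do. Taking eligible patients in order of treatment start removes the centre's discretion among eligible patients. It does nothing for patients whom the criteria remove beforehand.

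The justification in 9.9 suits usage and behaviour at home. It does not suit receipt. Someone treated only in hospital is still within the group that Table 1 says should be given the materials, and the brochure is written to be read before treatment begins. Whether such a person received it is a meaningful question that the survey cannot answer.

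At stake is what the final report may say about reach. Read with 9.2.2, a receipt percentage from outpatient-treated respondents could be presented as the percentage for all treated patients, with nothing reported on the size or make-up of the group left out.

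**Working it through.** **Step 1. Can any planned element carry the result to in-patient-only patients?**

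| Element | Section | Reaches them? |
|---|---|---|
| Consecutive selection | 9.2.2 | No. It applies to people who meet the selection criteria |
| Comparison of those who agree with those who refuse | 9.7.2.1 | No. Both groups are eligible people |
| Site log of patients given Blincyto | Study Design Schema, 9.2.2, 9.9 | Possibly, but it is described as holding age and sex, with no treatment setting |
| Limitations text | 9.9 | It discloses the exclusion but does not narrow the claim in 9.2.2 |

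Nothing planned supports the wider claim. Only the log comes near, and it could not separate the excluded group.

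**Step 2. What is the difference between the two populations?** The Protocol has no figure to reproduce here: the sample size and the confidence limits in Table 2 are redacted. Let

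- f = share of treated patients who were in-patient only (not given; assumed 10% to 50%);
- r_out = receipt among those treated as outpatients (60% and 90%, the ends of the planning range in 9.5);
- r_in = receipt among in-patient-only patients (not given; taken from 0% to 100%).

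Receipt among all treated = (1 − f) × r_out + f × r_in.

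Difference = r_out − receipt among all treated = f × (r_out − r_in).

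Example: f = 20%, r_out = 60%, r_in = 30% gives 0.20 × (0.60 − 0.30) = 6 points, so 60% becomes 54%.

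Difference in percentage points (positive means that the survey figure is higher than the figure for all treated):

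| r_out | f | r_in = 0 | r_in = half of r_out | r_in = r_out | r_in = 100% |
|---|---|---|---|---|---|
| 60% | 10% | 6 | 3 | 0 | −4 |
| 60% | 20% | 12 | 6 | 0 | −8 |
| 60% | 50% | 30 | 15 | 0 | −20 |
| 90% | 10% | 9 | 4.5 | 0 | −1 |
| 90% | 20% | 18 | 9 | 0 | −2 |
| 90% | 50% | 45 | 22.5 | 0 | −5 |

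**Step 3. When would a majority among outpatients not be a majority among all treated?** Set the all-treated figure to 50% and solve for f.

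- r_in = 0: f = 1 − 0.5 / r_out. This is 16.7% at r_out = 60% and 44.4% at r_out = 90%.
- r_in = half of r_out: f = (r_out − 0.5) / (0.5 × r_out). This is 0.10 / 0.30 = 33.3% at 60% and 0.40 / 0.45 = 88.9% at 90%.

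Near 60% a majority reading for all treated patients could turn on the excluded group. Near 90% it could not, unless that group is large. If receipt does not depend on setting, nothing changes at any f.

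**The case against.** The strongest reply is that the exclusion is open and reasoned. It stands in the Abstract, the criteria and the Limitations, so a reader knows who was surveyed. The success statement in the Abstract and in 8.2 refers to a majority of those taking part in the survey, read with response rate, recruitment and outside information; it is not tied to all treated patients. The study population in 9.7.2.3.1 heads a nested list that narrows at the next line, so it works as a source population rather than a rival definition of who is analysed. In Table 1, the capitals in the target column abbreviate the disease and do not mean every patient. All of this stands. It limits the point to the claim in 9.2.2 and the label in 9.7.2.3.1, but it does not make the claim true.

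A reader might go further and infer that the receipt percentage is probably too high for all treated patients, because patients who never go home are sicker or because centres hand the materials over at discharge. The documents do not support this. Hand-over at discharge is mentioned nowhere. No section gives receipt by setting or the in-patient-only share. Section 7.1 asks for provision to all expected users, and the brochure is written for reading before treatment, which section 7.1 recommends starting in hospital. If that is followed, receipt is the same in both settings and the difference is zero.

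**Conclusion.** The point holds as a mismatch between claim and design. The Protocol says that its results extend to all Blincyto-treated patients, while its criteria confine them to people with outpatient exposure and their caregivers, and the reasons in 9.9 do not cover receipt. What the survey can report is receipt among outpatient-treated people.

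The size is f × (r_out − r_in), and neither f nor r_in can be found in the document. Every value in the table rests on assumed f and r_in; zero is among the results, and so are negative values. No direction of bias is established, and the calculation shows only that the gap cannot be assumed negligible when receipt is near 60%. The patient figures also do not transfer directly to caregivers, who are analysed separately and would have their own share and receipt rate.

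**What to change.** - **9.2.2:** limit the generalisability statement to patients who receive Blincyto as outpatients and their caregivers.
- **9.7.2.3.1:** label the first set the source population.
- **9.9:** state that receipt is not estimated for in-patient-only patients.
- **Site log:** add an in-patient-only flag, and report the number, percentage, age and sex of these patients beside the receipt result.
- **Optional:** for patients, show a worst-case value that counts every in-patient-only patient as not having received the materials, (1 − f) × r_out, labelled as an extreme sensitivity analysis. It is imputed, because the log holds no receipt data.

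The cost is a few changes of wording, one field on a log that sites already keep, and a narrower claim.

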9.2.3 Subject Eligibility

9.2.3.1 Inclusion Criteria

- Patient/caregiver **completing questionnaire** is 18 years of age or older.
- Patient and/or caregiver of a patient with Ph- R/R B-precursor ALL who has received Blincyto **as an outpatient**.
- Patient/caregiver **completing questionnaire** can read and understand the native language of the country in which the study is being conducted.

9.2.3.2 Exclusion Criteria

- Patient and/or caregiver of a patient who has only received Blincyto as an in-patient **only**.
- Patient/caregiver is currently employed by Amgen/delegate.
- **Patient and/or caregiver of a patient who is participating in Blincyto clinical trials or is receiving Blincyto through a compassionate use program**

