Summary Table of Study Protocol

Summary Table of Study Protocol	A cross-sectional survey of patients and caregivers receiving Blincyto in routine clinical practice in Europe to evaluate the effectiveness of additional risk minimisation measures
Protocol version identifier	Amendment 1
Date of last version of the protocol	18 October 2016
EU Post Authorisation Study (PAS) Register No	EUPAS17829
Active Substance	Blinatumomab
Medicinal Product	Blincyto
Product Reference	H0003731
Procedure Number	NA
Marketing Authorisation Holder(s)	Amgen Europe B.V. [name]
Joint PASS	No

Research Question and Objectives	
The research question is whether additional risk minimisation measures introduced for the safe and effective use of Blincyto® (blinatumomab) are effective in patients with Philadelphia chromosome–negative (Ph-) relapsed/refractory (R/R) B-precursor acute lymphoblastic leukaemia (ALL) and their caregivers.
 
The primary objectives of the survey are to describe receipt of the educational materials and knowledge about key safety messages in the educational materials, among patients with Ph- R/R B-precursor ALL receiving Blincyto and their caregivers.
 
The secondary objectives of the survey are:
 
- To describe behaviours outlined in the educational materials, by patients with Ph– R/R B-precursor ALL receiving Blincyto and their caregivers.- To describe the level of understanding of key safety messages in the educational materials, among patients with Ph– R/R B-precursor ALL receiving Blincyto and their caregivers.- To describe usage of the educational materials, among patients with Ph– R/R B-precursor ALL receiving Blincyto and their caregivers.
Country(-ies) of Study	Target countries include France, Germany, Italy, Spain, United Kingdom, and potentially other European countries. The final list of countries will be dependent on country-specific factors including the timing of Blincyto launch and levels of usage.

Author	PPD [REDACTED] [REDACTED] [REDACTED] [REDACTED] [REDACTED] [REDACTED] [REDACTED] [REDACTED] [REDACTED] [REDACTED]
---------------	--

Marketing Authorisation Holder

Marketing authorisation holder(s)	Amgen Europe B.V. [name]
MAH Contact	PPD [REDACTED] [REDACTED] [REDACTED] [REDACTED]

Confidentiality Notice

This document contains confidential information of Amgen Inc.

CCI

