As a requirement linked to the Blincyto Risk Management Plan (RMP), Amgen as the Marketing Authorisation Holder (MAH), shall ensure that in each member state where Blincyto is marketed all healthcare professionals (HCPs) who are expected to prescribe, dispense or administer the product, and patients/caregivers who are expected to use the product, be provided with the aRMMs presented in Table 1.

Table 1. Blincyto aRMMs in the European Union

Measure	Target population	Key messages
Educational brochure for nurses	Haematology Nurses	
 Remarks on the importance of reporting adverse drug reactions (ADRs) Description of the administration procedures of Blincyto Description on patient's monitoring and management of early signs and symptoms of neurological events Recommendation for patients not to drive while receiving Blincyto and to contact immediately the treating physician / nurse if they experience neurological symptoms
Educational brochure for physicians	Haematologist Oncologist	
 Remarks on the importance of reporting ADRs Information on treatment with Blincyto, administration and posology, duration of hospitalisation, interruption and/or permanent discontinuation of the treatment
Educational brochure for pharmacists	Hospital Pharmacists	
 Remarks on the importance of reporting ADRs Detailed description of the reconstitution and preparation procedures of Blincyto infusion solution for intravenous administration, using aseptic techniques
Educational brochure for patients/caregivers	ALL patients receiving Blincyto and their caregivers	
 Remarks on the importance of reporting ADRs Description of the administration procedures of Blincyto and how to reduce the risk of MEs while using the infusion pump. Description of the main signs and / or symptoms of neurologic events and the importance of notifying the treating physician or nurse immediately if symptoms occur Recommendation for patients not to drive while receiving Blincyto
Patient Card	ALL patients receiving Blincyto and their caregivers	
 Remarks on the importance of reporting ADRs A warning message for HCPs treating the patient at any time, including emergency conditions, that the patient is using Blincyto Contact details of the Blincyto prescriber Blincyto treatment start date

Effectiveness of Blincyto educational tools

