9.2.4 Baseline Period

This is a cross-sectional survey that does not involve any follow-up of patients and caregivers. Eligibility criteria will be assessed and patient/caregiver questionnaire completed at one point in time within the data collection period.

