9.3.1 Exposure Assessment

Patients included in the study will **have been exposed to blincyto: they will be asked about their experience of Blincyto educational materials. Questionnaires may be completed at first exposure or following first exposure (Figure 2)** . Caregivers of patients meeting the selection criteria will also be invited to participate.

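### The trial and compassionate-use exclusion is judged at the survey date but the answers refer to first home exposure, so patients who have since moved to marketed Blincyto are eligible and report on non-routine use

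*Protocol*

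**What the plan says.** The target is set by the title: "A cross-sectional survey of patients and caregivers receiving Blincyto in routine clinical practice in Europe". Section 7.1 ties the duty to provide the materials to marketed use: the holder "shall ensure that in each member state where Blincyto is marketed all healthcare professionals (HCPs) who are expected to prescribe, dispense or administer the product" receive them. The same duty covers the patients and caregivers expected to use it.

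Four statements then decide who answers, and about what.

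- **Inclusion (section 9.2.3.1):** "Patient and/or caregiver of a patient with Ph- R/R B-precursor ALL who has received Blincyto", completed by the condition that this was as an outpatient. It covers any past outpatient use and does not restrict the source of supply.
- **Exclusion (section 9.2.3.2, and the abstract in section 4):** "Patient and/or caregiver of a patient who is participating in Blincyto clinical trials or is receiving Blincyto through a compassionate use program". Earlier participation is not mentioned.
- **When eligibility is judged (section 9.2.4):** "Eligibility criteria will be assessed and patient/caregiver questionnaire completed at one point in time within the data collection period".
- **What the answers refer to (section 9.2.2, note to Figure 2):** "Patients/Caregivers will complete the questionnaire based upon their first exposure to Blincyto at home". The note continues: "However, the questionnaire may be administered subsequent to blincyto cycle 1". Section 9.3.1 likewise allows completion at or after first exposure.

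**The concern.** The exclusion exists to keep trial and access-programme users out of a survey of routine practice. It tests their status on the day of the form, while the form asks about an earlier period. Someone can pass the test and still describe the kind of use that the exclusion is meant to remove.

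Receipt of the brochure and card is a primary endpoint. Section 8.2 reads the measures as successful if a majority of respondents confirm receipt and have knowledge of the key messages. A respondent whose first home use was outside routine supply may truthfully report no brochure or card without any failure of the routine programme. Equally, that person may have been given the same or other materials. In either case the answer does not measure the routine programme. The same applies to the secondary endpoints of usage and behaviour.

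**Working it through.** The protocol has no figure to reproduce here. The check is to apply the criteria, as written, to specific patients. Assume that age, language and employment conditions are met.

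1. **Form filled in during the programme.** A patient goes home in cycle 1 on compassionate-use supply and completes the form in that cycle. Outpatient use: yes. Now in a programme: yes. Result: excluded, as intended.
2. **Same patient, form filled in after a change of supply.** From cycle 2 the supply is marketed drug, and the form is completed during home treatment in cycle 2. Outpatient use: yes. Inpatient only: no. Now in a trial or programme: no. Result: eligible. The answers refer to first home exposure, which is cycle 1 under the programme. The first home exposure is the same as in case 1; only the date of the form has changed.
3. **Earlier trial exposure as an inpatient only, first home use routine.** Eligible, and properly so, because the answers concern routine use.
4. **Only outpatient exposure was in a finished trial.** The criteria taken alone admit this person. The Study Design Schema, however, has the form completed before treatment ends, and section 9.9 restricts completion to ambulatory treatment after discharge. The case is therefore unlikely.

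Case 2 is the gap.

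**Is there time for it within one course?** Section 7.1 describes 2 initial cycles and up to 3 more, each of 4 weeks, separated by 2-week intervals. The longest such course is 5 × 4 + 4 × 2 = 28 weeks. Section 9.2.1 says that launch is staggered, and section 9.2.2 samples centres that prescribe or are expected to prescribe after launch. A change from programme to marketed supply between cycles is therefore possible. The protocol does not say that it happens, or how often.

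**Do the listed variables show it?** The covariates in section 9.3.3, the log fields in section 9.2.2 (age and sex) and the subgroups in section 9.7.2.5.1 do not include the supply setting. Days on Blincyto may show a long exposure, but not who supplied it.

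**Which endpoints are reached?** Receipt, usage and behaviour, through the reference to first home exposure. Section 9.9 says that responses should rest on what respondents know now, so knowledge is reached only if something learned earlier has carried over.

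**Size.** Let q be the share of affected respondents and d the difference in receipt, in percentage points, between them and routine users with receipt r. Overall receipt is (1 − q) × r + q × (r + d) = r + q × d, so the shift is q × d. As d lies between −100 and +100, the shift cannot exceed 100 × q points in either direction. The protocol gives neither q nor d. On purely assumed values:

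- d = −60 (20% against 80%): q = 5% gives 0.05 × (−60) = −3 points; q = 20% gives 0.20 × (−60) = −12 points.
- d = +15 (95% against 80%): q = 5% gives 0.05 × 15 = +0.75 points; q = 20% gives 0.20 × 15 = +3 points.

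These values show only that the sign and the size both depend on unknown inputs. They are not estimates for this survey.

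**The case against.** The best defence is that the protocol surveys people on a current course. Section 9.7.2.3.1 defines the study population as adults initiating Blincyto, or their caregivers. Sections 9.2.2 and 9.9 recruit consecutively by initiation date, with a log to check this. The form is completed before treatment ends. On that reading the present tense describes the course being surveyed, and most earlier trial courses fall outside. Figure 2 itself is not shown, and its note, which mentions cycle 1, may mean first home use within the current course. The questionnaire is a separate document with a screening section, so it may ask more than the protocol lists.

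Much of this stands. The number affected is probably limited, and reaching back to a separate earlier course is an interpretation, not something the note states. It does not close case 2. That patient is an initiator, is still on treatment and is within one course. None of the provisions requires first home use to be on marketed supply. Screening against the criteria as written would pass this patient.

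Three stronger readings are tempting and are not supported:

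- A reader might infer that people whose only home use was in a finished trial will enter in number. The criteria alone would allow it, but the timing and recruitment rules make it unlikely.
- A reader might infer that these respondents were trained differently and so raise the knowledge score. The protocol does not describe training or materials in trials or access programmes, and the knowledge items concern current knowledge.
- A reader might put a share and a percentage-point bias on the problem. No passage supplies either.

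**Conclusion.** The timing mismatch is real on the text: eligibility follows the supply at the survey date, while the answers follow the supply at first home exposure. It admits patients, and their caregivers, who began home treatment under trial or compassionate-use supply and changed to marketed drug before completing the form. Receipt, usage and behaviour are exposed directly; knowledge only by carry-over.

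The size and direction are unknown. The effect is zero if nobody changes supply before answering. The conclusion rests on reading the exclusion literally at the single assessment point in section 9.2.4, and on taking the Figure 2 note to cover at least the current course. This is a cheap improvement that brings the criterion into line with the routine-practice question. It does not demonstrate bias.

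**What to change.** Preferred: in sections 4 and 9.2.3, require that the patient's first outpatient (home) exposure, on which the answers are based, was to marketed Blincyto in routine practice. For caregivers, apply this to the patient they support. This tests the same period that the form asks about and keeps eligible those whose earlier trial exposure was inpatient only. A blanket exclusion of anyone ever in a Blincyto trial would remove those valid respondents from an already small orphan population.

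Alternative: leave eligibility as it is, record the supply setting of the first home exposure on the site log, and report the primary endpoints with and without respondents whose first home use was under a trial or compassionate-use programme.

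The first option costs a few words in two sections and possibly a few respondents. The second costs one log field and one extra presentation of the primary endpoints, and loses no one.
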